## PURPOSE AND OBJECTIVES

**Purpose:** The importance of the research and the potential knowledge to be gained should be explained in detail. Give background information.

Multiple studies have shown that perioperative communication is important in reducing family member anxiety and improving the overall experience of family members waiting for surgical patients. In fact, perioperative communication and attentiveness have been identified as the two most important determinants of perceived surgeon performance. Moreover, surgeons agree that perioperative communication is important and report feeling as though the patients' family members are pseudo-patients, requiring attention and treatment, and perceive reduced family anxiety as a necessary component toward understanding post-operative status updates and findings.

Communication and empathy is even more important in the case of adverse outcomes. Family members of ICU patients rated attitude, clarity of message, and ability to ask questions as most important when receiving bad news. The CARE/SHARE models of establishing rapport with patients and families suggests it is best to wait until all information is available before speaking with the family, particularly in the event of adverse surgical outcomes. However, presently there is no agreed upon standardized time to deliver post-operative news to patients' families, with some surgeons delivering news before a procedure is entirely complete.

We have identified several times at which different surgeons deliver news in the perioperative period: 1) As soon as the major part of the procedure is completed, 2) While the patient is sutured at the close of the surgery, 3) Once the patient is extubated, and 4) Once all auxiliary information is obtained (x-rays, neurovascular examination, etc.) and the patient is awake. While there is anecdotal evidence that it may be concerning to patients' families to not receive an update at the scheduled ending time of a procedure, actual family preference remains undetermined. In a study by Blum et al, families were surveyed regarding perioperative stress and experience satisfaction. Those receiving periodic updates from a circulating nurse (calling every two hours) reported less anxiety and a better overall experience than the group of families who did not receive periodic updates. However, no study currently exists that examines the optimal timing and level of detail of surgeon-family communication.


**Objectives:** *Clearly state the primary and secondary objective(s) of the study.*

With a focus on patient and family centered care, we aim to determine the effect of strategic communication with patients' relatives during the perioperative period on their satisfaction, anxiety and overall experience. We hypothesize that the greatest patient and family satisfaction would come from receiving critical strategic updates during vital time points of the surgical procedure.

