**Family Member Demographic Information**

Age: \_\_\_\_\_

Sex (circle one): F / M / Other

Highest educational degree you have attained (check one):  High School diploma or equivalent (GED)  
 Associate degree  
 Vocational degree  
 Bachelor's degree  
 Master's degree  
 Professional degree  
 None of the above

1. How are you related to the patient (i.e parent, spouse, partner, son, daughter, etc)?

2. Please rate your level of satisfaction with your overall experience today in the perioperative area by circling the answer that best describes your satisfaction (with 1 being extremely unsatisfied and 5 being extremely satisfied).

|             |               |              |                 |               |                |
|-------------|---------------|--------------|-----------------|---------------|----------------|
| None at all | Extremely low | Somewhat low | Not high or low | Somewhat high | Extremely high |
| 0           | 1             | 2            | 3               | 4             | 5              |

3. Please rate your level of anxiety during the surgery by circling the answer that best describes your anxiety (with 0 being none at all and 5 being extremely high).

|             |               |              |                 |               |                |
|-------------|---------------|--------------|-----------------|---------------|----------------|
| None at all | Extremely low | Somewhat low | Not high or low | Somewhat high | Extremely high |
| 0           | 1             | 2            | 3               | 4             | 5              |

4. Please rate your level of satisfaction with the number of updates provided during the perioperative period (with 1 being extremely unsatisfied and 5 being extremely satisfied).

|             |               |              |                 |               |                |
|-------------|---------------|--------------|-----------------|---------------|----------------|
| None at all | Extremely low | Somewhat low | Not high or low | Somewhat high | Extremely high |
| 0           | 1             | 2            | 3               | 4             | 5              |

5. Please check all that apply regarding the frequency of updates you received during the perioperative period.

Updates were too frequent  
 Updates were too infrequent  
 I was satisfied with the number of updates I received

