### PROTOCOL SUMMARY

Project Title:

Protocol Version Date:

Perioperative Surgeon-Family Communication

4/14/16

Principal Investigator: [name]

Grant Sponsor: N/A

Grant Number: N/A

(For grants routed through UVM, indicate the OSP Proposal ID # located at the top of the OSP Routing Form)

**Lay Language Summary:** (Please use non-technical language that would be understood by nonscientific IRB members to summarize the proposed research project. The information must include: (1) a brief statement of the problem and related theory supporting the intent of the study, and (2) a brief but specific description of the procedure(s) involving the human subjects. Please do not exceed one single-spaced 8 1/2 X 11" page.)

It has been shown that perioperative communication plays an important role in reducing family member anxiety and improving overall satisfaction while they are waiting for surgical patients. As the notion of patient and family centered care has evolved over the years, it has become clear that patients' family members require attention and care during the perioperative period. Studies have suggested that family members who received periodic updates during their loved ones' surgeries report less anxiety and a better overall experience than families who do not receive the periodic updates. However, there have been no studies conducted that investigate the optimal timing and level of detail of the surgeon-family communication. The proposed study aims to determine the effect of strategic communication with patients' relatives during the perioperative period on their satisfaction, anxiety and overall experience. We hypothesize that the greatest patient and family satisfaction would come from receiving critical strategic updates during vital time points of the surgical procedure.

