**Not applicable**

The paper survey will be administered after the final update has been received by the family in the waiting area. A member of the research team will deliver the survey to the family member, and there will be a collection box in the waiting area for the completed surveys. There will be no identifying information on the survey. The survey will be administered only once per family, and it has a total of six questions.

**Statistical Considerations:** Delineate the precise outcomes to be measured and analyzed. Describe how these results will be measured and statistically analyzed. Delineate methods used to estimate the required number of subjects. Describe power calculations if the study involves comparisons. Perform this analysis on each of the primary and secondary objectives, if possible.

We will be examining the relationship between patient families' levels of anxiety and satisfaction with the number of updates received during the perioperative period. We will include a minimum of 96 participants, with 48 cases in each study group. This study sample was chosen using previous data collected in a similar study. Although this study did not administer surgical updates at specific time points, as we propose, they used a similar method of analyzing anxiety and satisfaction levels. Using their mean anxiety ratings, along with the standard deviations, a power analysis revealed that for a power of 0.8 with a significance of 0.05, the proposed study will require a total of 96 participants.

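### No primary outcome is named: the only hypothesis is on satisfaction, the only power calculation is on anxiety, and the survey has two satisfaction ratings

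*Combined protocol and SAP*

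**What the plan says.** The form's instruction under Objectives is "Clearly state the primary and secondary objective(s) of the study". The answer gives one aim, the effect of strategic communication on relatives, "on their satisfaction, anxiety and overall experience". Nothing is labelled primary or secondary.

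The only hypothesis follows: "We hypothesize that the greatest patient and family satisfaction would come from receiving critical strategic updates during vital time points". The Lay Language Summary states it too ("We hypothesize that the greatest patient and family satisfaction would come from receiving critical strategic updates"). It concerns satisfaction alone. It mentions patient satisfaction as well, although only a family member completes the survey.

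Statistical Considerations describes the outcomes as "levels of anxiety and satisfaction with the number of updates received during the perioperative period". Its sample size is at least 96, 48 per group, for power 0.8 at significance 0.05. The basis is a prior study: "Using their mean anxiety ratings, along with the standard deviations, a power analysis revealed" that number. Those means and SDs are not reproduced, and the section concedes that "this study did not administer surgical updates at specific time points, as we propose". It gives no between-group test, sidedness, order of testing or multiplicity rule. Number of Subjects keeps the minimum of 96 and anticipates about 200.

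The survey has three rating items. Question 2 begins "Please rate your level of satisfaction with your overall experience today in the perioperative area", question 3 rates anxiety during surgery, and question 4 rates satisfaction with the number of updates.

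**The concern.** The stated hypothesis has no stated power, and the outcome that was powered has no stated hypothesis. A reader cannot tell which result decides whether the updates worked.

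Three things are at stake.

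- **Error rate.** A significant result on question 2, 3 or 4 could each be presented as the trial's finding at 0.05, so the overall chance of a false positive exceeds 5%.
- **Conflicting results.** If one outcome is significant and another is not, the plan does not say which prevails. Any choice made after results by group are known would not be credible.
- **Interpretation of the sample size.** The 80% applies to an anxiety effect that is not shown. What satisfaction difference 96 participants could detect is not stated.

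**Working it through.** **Inputs from the protocol.** 96 participants, 48 per group, power 0.8, significance 0.05 (Statistical Considerations); about 200 anticipated (Number of Subjects). No effect size, SD, sidedness or correlation is given. Effects (in SD units) and correlations below are therefore assumptions, and 100 per arm assumes an equal split of 200 with every survey completed.

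**1. The plan's own figure.** The anxiety means and SDs are not in the document, so 96 cannot be reproduced forward. It can only be solved backwards for the effect it implies:

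d = (z for 1 − α/2 + z for power) × √(2/n) = (1.960 + 0.842) × √(2/48) = 2.802 × 0.2041 = 0.572

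With the t distribution this is 0.578 two-sided, or 0.511 one-sided. At 100 per arm the two-sided t value is 0.398. So 96 is a possible answer, but it can be neither confirmed nor refuted.

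**2. Power for satisfaction** (two-sample t-test, two-sided 0.05).

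| Assumed effect (SD) | Power, 48 per arm | Power, 100 per arm | Total for 80% power |
|---|---|---|---|
| 0.3 | 31% | 56% | 352 |
| 0.4 | 49% | 80% | 200 |
| 0.5 | 68% | 94% | 128 |
| 0.6 | 83% | 99% | 90 |
| 0.8 | 97% | not calculated | 52 |

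**3. False positives if each outcome is tested at 0.05 and the updates have no effect.** Under independence the rate is 1 − 0.95^k: 1 − 0.95² = 9.75% for two outcomes and 1 − 0.95³ = 14.26% for three. Numerical integration with equal correlations gives the other columns.

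| Outcomes tested | Correlation 0 | 0.5 | 0.8 |
|---|---|---|---|
| Two | 9.8% | 9.1% | 7.8% |
| Three (questions 2, 3, 4) | 14.3% | 12.5% | 9.8% |

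**4. Disagreement when the updates help on both outcomes.** Suppose anxiety and one satisfaction item both truly improve by 0.578 SD, so each has 80% power at 48 per arm. If they were independent, exactly one would be significant in 2 × 0.8 × 0.2 = 32% of trials. With correlation 0.3, 0.5 and 0.7 the figures are 27%, 23% and 18% at 48 per arm, and about 3% at 100 per arm (200,000 simulated trials each).

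**5. Which item is satisfaction?** The wording in Statistical Considerations can be read as question 4. It can also be read as relating both anxiety and satisfaction to the number of updates. Question 2 is worded as satisfaction too, but its subject is overall experience, which the aim lists separately. The Procedures section refers only to satisfaction and anxiety levels. The text does not settle the item.

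**The case against.** Anxiety is a declared outcome: it is in the aim and in the description of the study given to families. Sizing the trial on it is therefore not foreign to the objectives. This is right, and it narrows the defect to unranked outcomes, with the hypothesis and the power statement resting on different ones. That is still enough to leave the decisive result undefined.

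The three listed outcomes could map onto the three items, with question 4 as satisfaction, question 3 as anxiety and question 2 as overall experience. This is plausible but not conclusive, for the reasons in step 5 of the working.

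The plan never says that all three items will be tested at 0.05; that level appears only in the sample-size sentence. So 7.8% to 14.3% describes what the plan permits, not an analysis it specifies. This stands as a qualification.

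The 23% disagreement rate assumes equal effects of 0.58 SD, which nothing supports for satisfaction, and it falls to about 3% at 200. Naming a primary outcome would not lower it; it would only settle which result decides. That too stands. The false-positive excess, however, does not shrink with sample size, and the protocol commits only to 96.

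The power figures treat single ordinal items as normally distributed. Taking 200 as completed surveys is also optimistic, because families who decline the survey are removed. Both are limits on precision and leave the conclusion unchanged.

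**Conclusion.** The concern holds and must be fixed. No primary outcome is named, the hypothesis and the power calculation concern different outcomes, and the satisfaction item is not identified.

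The plan permits a false-positive rate of 7.8% to 9.8% with two outcomes and 9.8% to 14.3% with three, over assumed correlations from 0.8 to 0. At the committed minimum of 96, satisfaction has 80% power only if its effect is about 0.58 SD or larger (two-sided t-test). The document gives no satisfaction effect against which to judge that.

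The verdict does not say that 96 is wrong. It says that 96 belongs to anxiety and cannot be verified from the document. The textual part of the finding rests on no assumption.

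**What to change.** Before any outcome is examined by group, amend the protocol as follows.

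1. Name one primary outcome by survey question number, tested at two-sided 0.05, and make the hypothesis and the power statement refer to that item. The choice belongs to the investigators.
2. If it is anxiety (question 3), the existing calculation fits; write the means and SDs behind 96 into the protocol.
3. If it is satisfaction, choose question 2 or question 4 and state its own assumed difference, SD, power and sample size.
4. Label the other items secondary. Either test them in a stated fixed order after the primary, or report them with confidence intervals and no confirmatory claim.
5. State the scale of the chosen item. Questions 2 and 4 describe 1 to 5 in the stem but print 0 to 5; question 3 is 0 to 5, while Procedures says 1 to 5.
6. State the detectable effect for the planned number of completed surveys: 0.58 SD at 96, 0.40 SD at 200.

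**Cost.** One amendment and no new data collection, unless satisfaction is chosen with an effect too small for the planned number (last column of the power table).

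If anxiety is primary with fixed-order testing, satisfaction loses power. The table assumes 0.5 SD on questions 2 and 4 and all correlations 0.5 (200,000 simulated trials).

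| Per arm | Tested alone | Anxiety effect | Second in order | Third in order |
|---|---|---|---|---|
| 48 | 68% | 0.58 SD | 60% | 49% |
| 48 | 68% | 0.4 SD | 41% | 35% |
| 100 | 94% | 0.58 SD | 93% | 89% |
| 100 | 94% | 0.4 SD | 78% | 76% |

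Reporting the secondaries with confidence intervals only avoids this loss, but gives up a confirmatory claim on the one hypothesis the protocol states.

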## METHODS AND PROCEDURES

**Study Design:** *Describe the research design, including a description of any new methodology and its advantage over existing methodologies.*

This is a survey-based study. The survey has been adopted from a previously validated survey, and modified accordingly.

**Procedures:** *Describe all procedures (sequentially) to which human participants will be subjected. Identify all procedures that are considered experimental and/or procedures performed exclusively for research purposes. Describe the types, frequency and duration of tests, study visits, interviews, questionnaires, etc. Include required screening procedures performed before enrollment and while on study. Please provide in table, list or outline format for ease of review. (describe and attach all instruments)*

**Note:** *A clinical research protocol may involve interventions that are strictly experimental or it may involve some aspect of research (e.g., randomization among standard treatments for collection and analysis of routine clinical data for research purposes). It is important for this section to distinguish between interventions that are experimental and/or carried out for research purposes versus those procedures that are considered standard therapy. In addition, routine procedures performed solely for research purposes (e.g., additional diagnostic/follow-up tests) should be identified.*

Prior to the surgery, a member of the research team will review each case to determine if the surgery meets study criteria. The exclusion criteria include: surgeries lasting less than two hours, patients under the age of 18, non-speaking patients and/or families, or patients that do not have family members present in the pre-operation area. On the day of the surgery, a research team member will inform the patient and family that a study is being conducted to investigate the effect of perioperative communications on family satisfaction and anxiety. It will be explained that each family will randomly be assigned to two communication pathways, and there will be a short survey for them to complete post-surgery. In the control pathway, the surgeon will communicate with the family per his/her usual practice near the completion of the surgical procedure. In the intervention group, the families will receive additional standardized electronic updates via pagers at three pivotal moments: 1) Initial skin incision has been made, 2) Critical part of the case is completed and closure has begun, 3) Closure is complete, and patient is about to be transferred to the recovery room. A member of the surgical team will be responsible for sending these updates. Then, the surgeon will communicate the final update near the end of the surgical procedure per his/her usual practice.

After the surgery is complete, and both control and intervention groups have received the final update, a research team member will locate the waiting family and administer the post-operative survey rating their satisfaction and anxiety levels using Likert scale questions (1-5 scale). We adopted a previously used survey and modified it accordingly. In addition to the survey, basic demographic information of the patient and family member completing the survey, as well as the number of people in the waiting party, will be reported. When the family member has completed the survey, they will leave the survey in a secure drop box in the waiting area.

To ensure that the results of the survey are reproducible, we will take twenty subjects who completed the survey and ask permission to call them one day after the initial survey. We will then compare the results of the two surveys.

**For research involving survey, questionnaires, etc.:** *Describe the setting and the mode of administering the instrument and the provisions for maintaining privacy and confidentiality. Include the duration, intervals of administration, and overall length of participation. (describe and attach all instruments)*

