**E. Provide a description and justification for the requested change(s) listed in Section C. above.**

Research Protections Office, [name], [contact]

**Changes in Protocol Procedures:** Although the survey questions have been drafted using previously validated surveys, due to necessary modifications, we believe we should test the reproducibility of this study. To do so, we will administer the survey via telephone to twenty participants one day after the initial administration of the survey (which they will complete in the waiting room, as all other participants will do). We will use this information to confirm that the results of the study are reproducible.

**Survey Changes:** We have added age, socioeconomic status, and sex to the survey. We believe that the demographic information may affect the levels of satisfaction and anxiety of the family members, and this would be valuable information to obtain. In addition, University of Vermont Medical Center has launched a new website that allows family members to track their family members during the perioperative period. Access to this website may affect the levels of anxiety. We have added a question to the survey asking if they were aware of this website, and if so, if they made use of it.

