**For Research Team to complete:**

Date of Procedure:

Time into OR:

Time out of OR:

Length of the procedure:

Type of Procedure:

Surgeon:

Spinal vs. GA:

Group:

Thank you for taking the time to take part in our survey! The data from this study will allow us to identify family preferences regarding updates from the surgical team. This information can then be used to improve patient and family satisfaction in the perioperative period.

*Family Member Demographic Information*

Age: \_\_\_\_\_

Sex (circle one): F / M / Other

Highest educational degree you have attained (check one):  High School diploma or equivalent (GED)  
 Associate degree  
 Vocational degree  
 Bachelor's degree  
 Master's degree  
 Professional degree  
 None of the above

1. How are you related to the patient (i.e parent, spouse, partner, son, daughter, etc)?

2. Please rate your level of satisfaction with your overall experience today in the perioperative area by circling the answer that best describes your satisfaction (with 1 being extremely unsatisfied and 5 being extremely satisfied).

|             |               |              |                 |               |                |
|-------------|---------------|--------------|-----------------|---------------|----------------|
| None at all | Extremely low | Somewhat low | Not high or low | Somewhat high | Extremely high |
| 0           | 1             | 2            | 3               | 4             | 5              |

3. Please rate your level of anxiety during the surgery by circling the answer that best describes your anxiety (with 0 being none at all and 5 being extremely high).

|             |               |              |                 |               |                |
|-------------|---------------|--------------|-----------------|---------------|----------------|
| None at all | Extremely low | Somewhat low | Not high or low | Somewhat high | Extremely high |
| 0           | 1             | 2            | 3               | 4             | 5              |

4. Please rate your level of satisfaction with the number of updates provided during the perioperative period (with 1 being extremely unsatisfied and 5 being extremely satisfied).

|             |               |              |                 |               |                |
|-------------|---------------|--------------|-----------------|---------------|----------------|

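### Does the next-day repeat survey of twenty relatives need a named agreement statistic, a linking code and a corrected once-per-family sentence?

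*Combined protocol and SAP*

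**What the plan says.** The protocol's Procedures text (Methods and Procedures) says "we will take twenty subjects who completed the survey and ask permission to call them one day after the initial survey", and then "We will then compare the results of the two surveys". The amendment form, in its description and justification of changes, gives the mode and the purpose. The repeat is by telephone ("we will administer the survey via telephone to twenty participants one day after the initial administration of the survey"), it is added because validated surveys had to be modified, and "We will use this information to confirm that the results of the study are reproducible". Statistical Considerations does not mention the repeat.

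Three other statements bear on it:

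- The entry on survey administration says "There will be no identifying information on the survey" and "The survey will be administered only once per family".
- Procedures says of the completed paper form that "they will leave the survey in a secure drop box in the waiting area".
- The survey form ends with a block headed "For Research Team to complete", which records the date of the procedure, times into and out of the operating room, procedure type, surgeon, anaesthesia and group.

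**The concern.** Three things look open.

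1. The verb used for the analysis fixes no statistic, no items and no criterion. If it were carried out as a test of average scores, equal averages would be read as reproducibility even if individuals changed their answers freely.
2. Agreement can be computed only on linked pairs. The first form carries no identifier and goes into a drop box, and no code or log is described.
3. The once-per-family statement does not allow for the second administration.

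At stake is the one check that the investigators added to support a modified instrument. If it cannot fail, it gives no support.

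**Working it through.** **Inputs.** From the documents: 20 subjects, two administrations, items scored 0 to 5 on the form. The documents give no means, SDs or agreement levels for the repeat, and no derivation of the 20, so there is no planned figure to reproduce. Everything else below is assumed.

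**Step 1: what a test of means would show.** I simulated 20,000 studies of 20 pairs from a bivariate normal distribution, rounded and clipped to 0–5, with equal averages (mean 3, SD 1.2).

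| Correlation | Paired t-test, p ≥ 0.05 | Unpaired t-test, p ≥ 0.05 | Quadratic-weighted kappa, central 95% of estimates |
|---|---|---|---|
| 0 | 95% | 95% | −0.41 to 0.42 |
| 0.5 | 95% | 99% | 0.05 to 0.74 |
| 0.9 | 95% | about 100% | 0.66 to 0.94 |

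With mean 4 and SD 1.0, the paired result is again 95%, and kappa runs from −0.42 to 0.42 at correlation 0 and from 0.58 to 0.93 at 0.9. A p-value for the mean difference therefore says nothing about agreement. That follows almost by construction: a valid 5% test with no true shift is non-significant about 95% of the time at any correlation.

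**Step 2: does a person-by-person comparison work without a named coefficient?** Yes. In the first scenario, the central 95% of the SD of the within-person differences is 1.16 to 2.17 at correlation 0 and 0.45 to 0.86 at 0.9. These ranges do not overlap. Kappa, an intraclass correlation (ICC), exact agreement or limits of agreement would each separate no agreement from good agreement.

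**Step 3: what 20 pairs can deliver.** For a one-way ICC with two ratings, F = (1 + r)/(1 − r), and each limit is (F′ − 1)/(F′ + 1).

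- At an assumed observed r = 0.8, F = 1.8/0.2 = 9.
- Lower: F′ = 9/F(0.975; 19, 20) = 9/2.482 = 3.626, so the limit is 2.626/4.626 = 0.57.
- Upper: F′ = 9 × F(0.975; 20, 19) = 9 × 2.509 = 22.58, so the limit is 21.58/23.58 = 0.92.
- A lower limit of 0.5 needs F = 3 × 2.482 = 7.446, an observed ICC of 6.446/8.446 = 0.76.
- A lower limit of 0.7 needs F = (1.7/0.3) × 2.482 = 14.07, an observed ICC of 13.07/15.07 = 0.87.

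These limits assume normality and are approximate for 0–5 items. Kappa at this size does not separate moderate from good either: its central 95% range is 0.17 to 0.79 at correlation 0.6 and 0.47 to 0.89 at 0.8. Naming the statistic in advance would not narrow any of these intervals.

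**Step 4: can the forms be paired?** A research-team member delivers the form, each of the twenty must be asked in person for permission to call, and the team's block on the form records the date, operating-room times, procedure and surgeon. Together these would probably identify one case. A form without a name does not exclude a code or a separate contact list.

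**Step 5: the once-per-family sentence.** Its paragraph opens with the paper survey and describes the waiting-room form. The repeat is a telephone call, stated plainly in Procedures. One paper form per family and one call to twenty of those relatives can both hold.

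**The case for a change.** The strongest case for a change is that the investigators thought this check necessary, the protocol template asks how results will be analysed and at what intervals the survey is given, and the remedy is a few sentences plus a code on twenty forms. A form dropped in the box without a code might be hard to match later, and the handling of telephone contact details is not described. It is also true that no statistic, item list or criterion appears anywhere, that how the twenty are chosen (including by group) is not stated, and that moving from paper to telephone mixes a mode effect with retest variation.

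The omissions stand as facts. The harm does not follow from them. The failure shown in Step 1 belongs to an analysis that the plan never proposes. Naming kappa or an ICC would still leave confirmation undefined without a threshold, and 20 pairs would meet a demanding threshold only if agreement were very high. What does stand is a caution on language: the result will be an estimate with a wide interval, and the amendment's promise to confirm reproducibility is stronger than 20 pairs can usually bear.

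**Conclusion.** No change to the plan follows. The unnamed statistic and the undescribed link are missing detail in a small ancillary check, which an analyst would sensibly fill with a paired agreement measure and its interval. The once-per-family sentence is at most a clerical slip that misleads no one, because Procedures states the repeat outright. The check involves twenty people and does not enter the stated objective, the comparison of the two communication pathways, the minimum of 96 participants (48 per group) or safety.

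This rests on two readings: that the two surveys are compared within person, and that the team's procedure details are enough to match a call to its form. If matching failed, the check would be uninformative, but the trial's main result would be the same.
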